9.8.2 Biomarker assessments in tumor

Pre- and on-treatment PD-L1 expression will be assessed using the Dako PharmDx 28-8 assay. PD-L1 stained tissue sections will be assessed by a pathologist and membranous PD-L1 expression

[REDACTED]

In addition to PD-L1 assessment, the pre-treatment and on-treatment tumor sample may be used to assess other putative predictive and PD biomarkers of SC nivolumab to better characterize the TME.

[REDACTED]

9.8.3 Biomarker assessments in peripheral blood

A variety of biomarkers that may inform on [REDACTED] PD activity of nivolumab will be investigated in peripheral blood specimens taken from all participants prior to and during treatment. Several analyses will be completed and are described briefly below. Additional biomarker assessments may also be performed if samples are available.

[REDACTED]

9.8.3.2 Exploratory Serum [REDACTED] Biomarkers

Blood samples for exploratory serum [REDACTED] biomarker analyses will be drawn at the specified time points indicated in the biomarker tables (Table 9.8-1 and Table 9.8-2).

[REDACTED] Separate blood samples will be collected and processed for serum [REDACTED] and then put in frozen storage. Serum [REDACTED] samples may be assessed by ELISA

[REDACTED]

9.8.4 *Additional Research Collection*

For All US sites:

Additional research is required for all study participants except where prohibited by IRBs/ethics committees, or academic/institutional requirements. Where one or more of these exceptions occurs, participation in the additional research should be encouraged but will not be a condition of overall study participation.

- If the IRB/ethics committees and site agree to the mandatory additional research retention and/or collection, then the study participant must agree to the mandatory additional research as a requirement for inclusion in the study.
- If optional participation is permitted and approved, then the study participants may opt out of the additional research retention and/or collection.

For non-US sites:

Additional research is optional for all study participants, except where retention and/or collection is prohibited by local laws or regulations, ethics committees, or institutional requirements.

This collection for additional research is intended to expand the translational R&D capability at BMS, and will support as yet undefined research aims that will advance our understanding of disease and options for treatment. It may also be used to support health authority requests for analysis, and advancement of pharmacodiagnostic development to better target drugs to the right

patients. This may also include genetic/genomic exploration aimed at exploring disease pathways, progression and response to treatment, etc.

Sample Collection and Storage

All requests for access to samples or data for additional research will be vetted through a diverse committee of the study sponsor's senior leaders in Research and Development (or designee) to ensure the research supports appropriate and well-defined scientific research activities.

Samples kept for future research will be stored at the BMS Biorepository [REDACTED] or an independent, BMS-approved storage vendor.

Samples will be stored in a coded fashion, and no researcher will have access to the key. The key is securely held by the Investigator at the clinical site, so there is no direct ability for a researcher to connect a sample to a specific individual. Further details of sample collection and processing will be provided to the site in the procedure manual.

Table 9.8.4-1: Residual Sample Retention for Additional Research Schedule

Sample Type	Timepoints for which Residual Samples Will Be Retained
PK	All

Abbreviations:

PK = pharmacokinetic;

9.8.5 Immunogenicity Assessments

Samples for testing potential nivolumab and rHuPH20 immunogenicity will be collected per the PK and immunogenicity sampling schedule [REDACTED].

9.9 Medical Resource Utilization and Health Economics

Health Economics/Medical Resource Utilization and Health Economics parameters will not be evaluated in this study.

9.10 Patient-reported Outcomes

9.10.1 Patient Experience and Preference Questionnaire

In order to better understand experiences with and preferences for mode of nivolumab administration, participants will complete a Patient Experience and Preference Questionnaire at various time points during the study. The core questionnaire contains items assessing patient perceptions regarding the convenience and acceptability of the mode of administration, treatment-related symptoms, and satisfaction with treatment.

The questionnaire will be administered immediately following completion of the injection or infusion on Day 1 of treatment Cycle 1 and Cycle 2 in Part A and Part B, and on Day 1 Cycle 1 of Part C, Part D, and Part E.

9.10.2 Qualitative Patient Interviews

Qualitative interviews will be performed with participants to gather insights not covered by the Patient Experience and Preference Questionnaire. The interviews will be conducted via telephone by a trained interviewer using a semi-structured interview guide. They will be conducted in the participant's native language and will be audio recorded and transcribed for analysis using qualitative data analysis techniques. Interviews conducted in languages other than English will be translated to English prior to analysis. Interviews will be conducted within 14 days of completing Cycle 1 Day 1 and Cycle 2 Day 1 in Part A, Part B, and Part C. For Part D and Part E, interviews will be conducted within 14 days of completing Cycle 1 Day 1 or any other cycle thereafter, if not captured at Cycle 1 Day 1. Participation in the interviews is optional and will be subject to the availability of interview materials and the fluency of trained interviewers. Failure to complete either interview will not constitute a protocol deviation.

10 STATISTICAL CONSIDERATIONS

10.1 Sample Size Determination

Calculation of precision estimates is based on AUC(TAU).

In Part A and Part B, administration of SC nivolumab (BMS-986298) to 20 participants will provide █ % confidence that the range between █ % and █ % of the point estimate of geometric mean AUC(TAU) will encompass the true value. Administration of SC nivolumab (BMS-986298) to 10 participants will provide █ % confidence that the range between █ % and █ % of the point estimate of geometric mean AUC(TAU) will encompass the true value. These calculations assume that AUC is log-normally distributed with standard deviation of █ for log(AUC[TAU]), based on coefficient of variation estimates for IV nivolumab 480 mg of █ % for AUC.

In Part D, administration of 1200 mg SC nivolumab Q4W to 36 PK evaluable participants will provide █ % confidence that the range between █ % and █ % of the point estimate of geometric mean AUC(TAU) will encompass the true value. Administration of 1200 mg SC nivolumab Q4W to 10 PK evaluable participants will provide █ % confidence that the range between █ % and █ % of the point estimate of geometric mean AUC(TAU) will encompass the true value. This calculation assumes that AUC is log-normally distributed with standard deviation of █ for

$\log(AUC[TAU])$, based on an estimated coefficient of variation for nivolumab SC of █ % (for $AUC[TAU]$). Variability has been estimated via modelling and simulation.

In Part E, administration of 600 mg SC nivolumab Q2W to █ PK evaluable participants will provide █ % confidence that the range between █ % and █ % of the point estimate of geometric mean $AUC(TAU)$ will encompass the true value. Administration of 600 mg SC nivolumab Q2W to █ PK evaluable participants will provide █ % confidence that the range between █ % and █ % of the point estimate of geometric mean $AUC(TAU)$ will encompass the true value. This calculation assumes that AUC is log-normally distributed with standard deviation of █ for $\log(AUC[TAU])$, based on an estimated coefficient of variation for nivolumab SC of █ % (for $AUC[TAU]$). Coefficient of variation of █ % for $AUC(TAU)$ has been observed in interim analysis 4 for the 1200 mg SC nivolumab Q4W dosing regimen.

Precision of measurements were calculated by nQuery Advisor 7.0.

10.2 Populations for Analyses

For purposes of analysis, the following populations are defined:

- **All Enrolled Participants:** all participants who sign an ICF and are registered into the IRT. This is the dataset for disposition.
- **All Randomized Participants:** all participants who are assigned/randomized to any treatment arm in the study. This dataset will be used for efficacy analyses.
- **All Treated Participants:** all participants who receive at least 1 dose of nivolumab. This is the dataset for safety analyses.
- **PK Participants:** All treated participants with available PK data.
- **Evaluable PK Participants:** The Evaluable PK Participants population is a subset of the PK Participants Population who have adequate dosing and adequate nivolumab serum concentration time data for estimation of PK endpoints. All available derived PK parameter values will be included in the PK data set and reported, but only participants in the Evaluable PK Participants population will be included in the summary statistics and statistical analysis.
- **Immunogenicity Evaluable Participants:** All treated participants who have a baseline and at least 1 post-baseline immunogenicity assessment.

10.3 Statistical Analyses

The statistical analysis plan will be developed and finalized before database lock and will describe the selection of participants to be included in the analyses and the procedures for accounting for missing, unused, and spurious data. Below is a summary of planned statistical analyses of the primary and secondary endpoints.

A description of the participant population will be included in the reported statistical output, including subgroups of age, gender, race, and tumor type. Frequency distributions of gender and race will be tabulated by treatment. Summary statistics for age, body weight, height, and body surface area (BSA) will be tabulated by treatment.

10.3.1 Efficacy Analyses

All efficacy analyses are exploratory and will be described in the statistical analysis plan finalized before database lock.

10.3.2 Safety Analyses

Safety analyses will be performed on the All Treated Participants population. Descriptive statistics of safety will be presented using NCI CTCAE v.5 by treatment group.

Endpoint	Statistical Analysis Methods
Incidence of AEs, TRAEs, SAEs, TRSAEs, AEs/TRAEs leading to discontinuation, and deaths	All on-study AEs, TRAEs, SAEs, TRSAEs, and AEs/ TRAEs leading to discontinuation will be tabulated using worst grade per NCI CTCAE v.5 criteria by system organ class and preferred term. Frequency distribution of treated participants with AE using the worst CTC grade. Participants will only be counted: (1) once at the PT level, (2) once at the SOC level, and (3) once in the “total participant” row at their worst CTC grade, regardless of SOC or PT. Deaths will be summarized by treatment group.
Incidence of clinical laboratory test abnormalities	On study laboratory parameters including hematology, chemistry, liver function, and renal function will be summarized using worst grade NCI CTCAE v.5 criteria.
Incidence of AEs in the MedDRA Anaphylactic Reaction broad scope SMQ occurring within 2 days after study drug administration	Descriptive statistics will be presented using NCI CTCAE v.5 criteria by treatment group.
Incidence of events within the hypersensitivity/infusion reaction select AE category occurring within 2 days after any study drug administration	Descriptive statistics will be presented using NCI CTCAE v.5 criteria by treatment group.

Abbreviations: AE = adverse event; CTC = Common Terminology Criteria; MedDRA = Medical Dictionary for Regulatory Activities; NCI CTCAE v5 = National Cancer Institute Common Terminology Criteria for Adverse Events version 5; PT = preferred term; SAE = serious adverse event; SMQ = standardized MedDRA query; SOC = system organ class; TRAE = treatment-related adverse event; TRSAE = treatment-related serious adverse event.

10.3.3 *Pharmacokinetic Analyses*

Pharmacokinetic analyses will be conducted using non-compartmental analysis and, if appropriate, PPK analysis. These analyses will be used to characterize the PK of SC nivolumab in Part A, Part B, Part D, and Part E, as well as to inform future clinical trials using SC nivolumab. Analyses from Part A and Part B were used to inform dose selection for Part C, Part D, and additional treatment groups in Part B.

Primary Pharmacokinetic Analysis: PK parameters will be summarized by cycle (dose and route of administration). Evaluable PK parameters will be summarized as follows:

For Parts A, B, D, and E: Geometric means and coefficients of variation will be presented for Cmax, Ctau, and AUC(TAU). Means and standard deviations will also be provided. Medians and ranges will be presented for Tmax. Other exposure measures may be summarized as appropriate.

For Part C: Geometric means and coefficients of variation will be presented for Ctrough.

To assess the dependency on dose after subcutaneous administration of the SC nivolumab (BMS-986298) formulation, scatter plots of Cmax and AUC versus dose will be provided.

Population PK analysis will be conducted as appropriate to determine a subcutaneous dose for future nivolumab trials as outline in [Section 10.3.7.1](#).

10.3.4 *Immunogenicity Analyses*

All immunogenicity analyses will be performed on the immunogenicity-evaluable population.

Endpoint	Statistical Analysis Methods
Incidence of anti-nivolumab antibodies and neutralizing antibodies, if applicable.	Frequency distribution of baseline ADA-positive participants and ADA-positive participants after initiation of the treatment, as well as neutralizing antibody-positive participants will be presented. Baseline ADA-positive participant is defined as a participant who has an ADA-positive detected sample at baseline. ADA-positive participant is a participant with at least 1 ADA-positive sample relative to baseline after initiation of the treatment.
Incidence of anti-rHuPH20 antibodies and neutralizing antibodies, if applicable	Frequency distribution of baseline ADA-positive participants and ADA-positive participants after initiation of the treatment, as well as neutralizing antibody-positive participants will be presented. Baseline ADA-positive participant is defined as a participant who has an ADA-positive detected sample at baseline. ADA-positive participant is a participant with at least 1 ADA-positive sample relative to baseline after initiation of the treatment.

Abbreviations: ADA = anti-drug antibody; rHuPH20 = recombinant human hyaluronidase PH20.

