9.4.5 Suicidal Risk Monitoring

Not applicable.

9.4.6 *Imaging Safety Assessment*

Any incidental findings of potential clinical relevance that are not directly associated with the objectives of the protocol should be evaluated and handled by the Study Investigator as per standard medical/clinical judgment.

9.4.7 *Assessment of Subcutaneous Injection Site*

The Investigator or designated study staff will assess the proposed injection site for signs of local irritation and inflammation. The proposed injection site will be evaluated prior to all SC doses and approximately 60 minutes after the Cycle 1 Day 1 injection (Parts A, B and D) and following the first SC injection after transitioning to 1200 mg dose in Part C. Part E participants will be monitored for approximately 30 minutes following the [REDACTED] and [REDACTED] SC manual injections. Participants receiving subsequent SC injections may be monitored post injection as clinically warranted and at the discretion of the investigator. There will be five pre-specified injection site reactions of interest: injection site erythema; injection site pain, injection site pruritus, injection site hematoma, and injection site swelling. Injection site reactions will be recorded as AEs on the appropriate page of the CRF. In addition, all participants will be contacted approximately 24 hours after the first 2 SC injections for reporting of injection site reactions. The injection site will also be evaluated predose at the next dosing visit.

9.5 *Pharmacokinetics*

Full details on the clinical pharmacology aspects of nivolumab can be found in the nivolumab IB.

The PK of nivolumab (BMS-936558 and BMS-986298) will be derived from serum concentration versus time measurements. The PK parameters to be assessed include:

- Cmax: Maximum observed serum nivolumab concentration
- Tmax: Time to maximal concentration
- AUC(TAU): Area under the concentration-time curve over the dosing interval
- Ctau: Observed serum nivolumab concentration at the end of the dosing interval
- Ctrough: Trough observed serum nivolumab concentration

Individual participant PK parameter values will be derived by non-compartmental and, if appropriate, population PK methods by a validated pharmacokinetic analysis program. Actual times of collection will be used in all PK analyses.

9.5.1 *Pharmacokinetics and Anti-drug Antibody Sample Collection and Processing*

[REDACTED]

[figure not shown]

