APPENDIX 10 INJECTION SITE SELECTION AND PREPARATION AND ADMINISTRATION OF STUDY DRUG

Subcutaneous Injection Site Selection and Preparation:

Subcutaneous injections of nivolumab (BMS-986298) alone and nivolumab with rHuPH20 will be administered in the abdominal area. An abdominal site that is approximately at the level of the navel (as allowed by skin condition) and approximately 15 cm (minimum 10 cm) away from the margin of the navel should be selected. The lateral portion of the abdomen is preferred over the midline area. The selected site should include fatty tissue.

Subcutaneous injections of nivolumab (BMS-986298) alone by syringe pump and nivolumab (BMS-986298) with rHuPH20 manually by syringe will be administered in the abdominal area. An abdominal site that is approximately at the level of the navel (as allowed by skin condition) and approximately 15 cm (minimum 10 cm) away from the margin of the navel should be selected. The lateral portion of the abdomen is preferred over the midline area. The selected site as determined by the Investigator should include fatty tissue and be free of any skin disease, condition (including, but not limited to, scarring, tattoos, or stretch marks), or skin pigmentation that could interfere with an assessment of the injection site.

Administration of Subcutaneous Injection:

The subject should be in a semi-reclined position during the injection (ie, semi-Fowler's position: 30-45°) and in a supine position immediately following injection for the evaluation of the injection site (ie, laying flat on back).

After the injection site for subcutaneous administration has been chosen, the total dose of nivolumab (BMS-986298) with rHuPH20 will be administered as a single subcutaneous injection, while nivolumab (BMS-986298) alone will be administered as 1 to 4 injections as described briefly below.

[figure not shown]
- Wipe skin with alcohol to cleanse. Allow to dry.
- Gently pinch and lift the skin of the abdomen (ie, "tenting").

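### Section 10.3.2 gives no injection or exposure denominator and no common window, so crude incidences of 2-day and injection-site events in Parts D and E are not comparable, in either direction

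*Combined protocol and SAP*

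**What the plan says.** In section 10.3.2 the AE row describes a "Frequency distribution of treated participants with AE using the worst CTC grade" and adds that "Participants will only be counted: (1) once at the PT level, (2) once at the SOC level", and once in the overall row at the worst grade. The presentation is by treatment group.

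Two further endpoints are tied to dosing: "Incidence of AEs in the MedDRA Anaphylactic Reaction broad scope SMQ occurring within 2 days after study drug administration" and "Incidence of events within the hypersensitivity/infusion reaction select AE category occurring within 2 days after any study drug administration". For both, the method is only that "Descriptive statistics will be presented using NCI CTCAE v.5 criteria by treatment group". Whether the unit is the participant, the event or the administration is not stated.

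Section 9.4.7 says "There will be five pre-specified injection site reactions of interest" and "Injection site reactions will be recorded as AEs on the appropriate page of the CRF". Section 10.3.2 gives these reactions no row of their own and no combined summary, so the AE rule governs them.

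Sections 5.1 and 5.2 set the schedules. Groups 1-4 receive one SC dose and then IV nivolumab every 4 weeks, with later crossover to SC dosing in Part C. Part D is SC every 4 weeks and Part E is SC every 2 weeks. Treatment may last up to 104 weeks. Under section 10.3.8, interim analysis 5 takes place once every Part E participant has at least 6 months of follow-up, and it includes all parts up to the lock.

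**The concern.** An event defined by a 2-day window after dosing, or a reaction at an injection site, can arise only after an administration. The share of participants ever affected therefore rises with the number of administrations, which is set by the schedule and by time on treatment. Both differ between parts.

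Safety is a secondary objective, and Part E was added to characterise dosing every 2 weeks. The by-group tables are where a reader will set Part E beside Part D. Without a denominator or a common window, the same risk per administration can appear as a difference between regimens, and a true difference can be hidden.

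For Groups 1-4 there is also a problem of attribution. The 2-day endpoints are not limited to SC doses, so IV doses from Cycle 2 count. Section 10.3.2 does not say whether events after Part C doses stay with the original group.

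**Working it through.** **No plan figure to reproduce.** The documents give no event rate for these endpoints, and the precision figures in section 10.1 concern AUC and are redacted. As a check on the inputs, the group sizes in section 5.2 add up to the stated total: 22 + 45 + 36 + 36 = 139.

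**Inputs from the documents.** Part D: 36 participants, one injection per 4 weeks. Part E: 36 participants, one injection per 2 weeks. Maximum treatment: 104 weeks. Part D enrolment was complete at Protocol Amendment 04 (Figure 5.1-1, footnote c), the amendment that added Part E.

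**Assumptions.** A per-injection risk p of 1% to 5%, equal in both parts; independent injections; no drop-out; 24 weeks (six 4-week cycles) standing in for the 6-month minimum.

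**Formula.** P(participant counted at least once) = 1 - (1 - p)^k, with k injections.

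*Equal time, 24 weeks: k = 24/4 = 6 in Part D and 24/2 = 12 in Part E*

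| p | Part D | Part E | Ratio E/D |
|---|---|---|---|
| 1% | 1 - 0.99^6 = 5.9% | 1 - 0.99^12 = 11.4% | 1.94 |
| 2% | 1 - 0.98^6 = 11.4% | 1 - 0.98^12 = 21.5% | 1.89 |
| 5% | 1 - 0.95^6 = 26.5% | 1 - 0.95^12 = 46.0% | 1.74 |

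At 5% this is about 9.5 against 16.5 of 36 participants. With two Binomial(36) counts, the probability that Part E shows more affected participants is 0.95.

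*Clustering.* If reactions recur in the same people, the gap narrows. A beta-binomial model with p = 5% and within-participant correlation 0.1 gives 21.7% vs 33.2% (ratio 1.53). With correlation 0.3 it gives 15.7% vs 21.2% (ratio 1.35).

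*Unequal time, Part E at 24 weeks (k = 12)*

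| Part D time | k in D | Part D, p = 5% | Part E, p = 5% |
|---|---|---|---|
| 48 weeks | 12 | 46.0% | 46.0% |
| 72 weeks | 18 | 60.3% | 46.0% |
| 104 weeks | 26 | 73.6% | 46.0% |

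Break-even is where Part D has twice Part E's time on treatment. Beyond that, Part D looks worse. At 104 against 24 weeks and p = 5%, the probability that Part E shows fewer affected participants is 0.99. At p = 1% the figures are 23.0% and 11.4%.

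**Groups 1-4.** Over 24 weeks on treatment before any crossover, they have one SC dose plus five IV doses, so six windows for the 2-day endpoints, the same number as Part D. A single-dose figure (k = 1, so 1.0% at p = 1%) fits only injection-site reactions before Part C.

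**Other AEs.** For events driven by calendar time, for example 0.1 per 4 weeks, both parts give 1 - exp(-0.1 × 6) = 45.1% at 24 weeks. Dosing frequency adds nothing there; only length of follow-up matters.

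**After the fix.** At p = 5% over 24 weeks, Part D expects 36 × 6 × 0.05 = 10.8 events in 216 injections and Part E 36 × 12 × 0.05 = 21.6 in 432, both 5.0 per 100. Restricted to the first two injections, both give 1 - 0.95^2 = 9.8%.

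**The case against.** The strongest points against are these.

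- **Direction.** A reader might infer that Part E will look less tolerable than Part D. The documents do not support that. It requires similar time on treatment, but Part D enrolled earlier and the lock takes all data. Actual exposure is not reported, so the sign is unknown.
- **Scope.** A reader might infer that every safety endpoint is counted once per participant, or that AEs in general are distorted by dosing frequency. The counting rule is written only in the AE row, and the per-injection argument fits window-bound and injection-site events only.
- **Contrast with and without rHuPH20.** A reader might extend the point to this contrast. Groups 1 and 2, and Groups 3 and 4, share the same dose days. Appendix 10 says "nivolumab (BMS-986298) alone will be administered as 1 to 4 injections", but that belongs to the regimen under study.
- **Ascertainment.** Table 2-3 checks for injection reactions on Day 2 of every SC cycle in Parts A-D, but in Part E only after the first two injections. This lowers Part E's count and would bias a plain per-injection rate.
- **Regimen effect.** If more injections mean more people with a reaction, participant incidence describes that correctly. Dose and product also differ between Parts D and E, so a common p is hypothetical.
- **Status.** Section 10.3 presents itself as a summary, with a SAP to be finalised before database lock, and section 10.3.8 plans no formal comparison needing adjustment of the significance level.

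All of this stands as a limit on the claim. None of it supplies a like-for-like summary. The SAP text is not among the documents, and section 10.3.2 sets out the counting in detail without mentioning exposure.

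**Conclusion.** The point holds in a direction-neutral form. For the two 2-day endpoints and the injection-site reactions, crude incidence by group cannot be compared between Parts D and E, because neither the number of administrations nor the follow-up is aligned and no denominator is given.

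The possible distortion runs from Part E at about 1.7 to 1.9 times Part D's incidence (1.35 with strong clustering at 5%) to a reversed order when Part D has much longer exposure. These sizes are illustrations that rest on the assumed equal risk per injection and no drop-out. They do not predict what the trial will show. The consequence is a misread descriptive table, with no effect on any error rate, so this is a worthwhile low-cost improvement rather than a flaw in the design.

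**What to change.** Keep the participant-level tables and make these changes in section 10.3.2:

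1. State the counting unit for the two 2-day endpoints, and how events after IV and Part C doses are assigned in Groups 1-4.
2. Define a combined endpoint of any of the five injection-site reactions.
3. For that endpoint and the two 2-day endpoints, report incidence after the first SC dose in Groups 1-4, Part D and Part E, and after the first two SC injections in Parts D and E. This is the like-for-like summary, and it falls where injection reactions are actively checked in every part. Count by SC dose, since Groups 2 and 4 may need several injections per dose.
4. Add an exposure summary by part: number of administrations by route and time on treatment.
5. As secondary output, report events per 100 administrations by route, with a confidence interval that allows for clustering within participant (for example a participant-level bootstrap). Caveat the rate for injection-site reactions because of the unequal checking.
6. Use person-time rates, not per-injection rates, for other AEs.
7. Reconcile Table 2-3 with section 9.4.7, which describes the 24-hour contact for all participants after the first two SC injections.

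The cost is additional output. Administration details and AEs are already recorded on the CRF, and the 2-day endpoints already require AE timing relative to dosing, so no new data collection should be needed.
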